2.2 Violations and deviations

Important protocol deviations (PDs) will be listed and tabulated in the CSR for randomised subjects (i.e. not screening failures). These are defined as PDs which may significantly affect the completeness, accuracy and/or reliability of the study data, or which may significantly affect a subject's rights, safety or well-being. Important PDs in this trial will be grouped under one of the following categories:

- Subjects who did not meet the inclusion criteria
- Subjects who met the exclusion criteria
- Subjects who developed discontinuation criteria for study product but were not withdrawn from study treatment
- Subjects who met the discontinuation criteria for overall study withdrawal but were not withdrawn from study

- Subjects with investigational product deviations (e.g. who received the wrong treatment or an incorrect dose)
- Subjects who received the excluded concomitant medications
- Subjects with deviations related to study procedures
- Subjects with other potential important deviations

All important PDs will be identified and documented by the study team prior to unblinding of the trial. As far as possible, the occurrence of important PDs will be monitored (blinded) during the trial, with the emphasis on their future prevention.

Important PDs will not be used to exclude any subject from any analysis set, nor to exclude any data from subjects included in an analysis set.

The study Non-compliance Handling Plan (NHP) outlines the management of PDs and includes the proposed categories of PDs in this trial. Any PDs which are not defined as important or COVID-19 related will not be reported and discussed in the CSR.

3. PRIMARY AND SECONDARY VARIABLES

3.1 General definitions

3.1.1 Age calculation

Age will be derived from the date of informed consent - date of birth, rounded down to the nearest integer. For subjects in countries where date of birth is not recorded, the age as recorded in the eCRF will be used.

3.1.2 Definition of baseline

In general, the last non-missing measurement on or prior to the date of randomisation will serve as the baseline measurement for efficacy variables. If there is no value on or prior to the date of randomisation, then the baseline value will not be imputed, and will be set to missing.

In general, the last non-missing measurement prior to first dose of study treatment will serve as the baseline measurement for safety variables. If there is no value prior to first dose of study treatment, then the baseline value will not be imputed, and will be set to missing.

Where unscheduled/repeat assessments are relevant and exist for any subject at a particular visit specified below, they will also be considered in the baseline definitions, provided they remain prior to the date of randomisation (efficacy) or the date of first dose of study treatment (safety).

According to the anticipated scheduling in the protocol, the following specific rules for the various data captured are proposed:

For categorical baseline respiratory disease characteristics captured directly in the eCRF (e.g. captured as ‘yes’ or ‘no’), if ‘yes’ is indicated in any visit during enrolment (scheduled or unscheduled), ‘yes’ will be used.

For clinic visit spirometry variables, the latest measurement recorded prior to first dose of study drug will be used as baseline.

For daily assessments which are made in both morning and evening, the whole day is defined by the assessments in the evening and the following morning. The daily assessment will be considered missing if either evening or following morning is missing. However, some analyses may consider morning and evening separately.

For SGRQ, the value at the randomisation visit (Visit 3) will be used as baseline.

For CAT, the value at the randomisation visit (Visit 3) will be used as baseline. If the Visit 3 measurement is missing, the screening value (Visit 1) will be used as baseline instead.

For evaluating respiratory symptoms in chronic obstructive pulmonary disease (E-RS: COPD), data collected in the last 14 days prior to randomisation will be used to calculate the individual E-RS: COPD total and subscale baseline means. If more than 7 daily measures/scores (>50%) are missing, then baseline is set to missing.

For EXACT-PRO, the baseline total score will be the mean score for each subject over the 7 days prior to randomisation. A minimum of 4 days of data (>50%) is required for calculating the baseline total score. To allow for improvement or deterioration in disease state over the course of the trial, the baseline total score will be reset every 4 weeks in the absence of an EXACT-PRO defined event.

For rescue medication use and nights with awakenings due to COPD symptoms, baseline is defined as the mean from the last 14 days prior to the date of randomisation and will be derived from data collected on the evening of Study Day -14 to the morning of Study Day 1. The biweekly mean is calculated as the sum of all non-missing daily measures/scores over 14 sequential days, divided by the number of non-missing daily measures/scores. If more than 7 daily measures/scores (>50%) within the baseline period are missing, then baseline is set to missing.

For clinic visit FENO, the value at the randomisation visit (Visit 3) will be used as baseline. If the Visit 3 measurement is missing, the run-in value will be used as baseline instead.

For safety variables (vital signs, weight/Body Mass Index (BMI), haematology, clinical chemistry, urinalysis, 12-lead ECG), baseline will be defined as the latest non-missing assessment prior to first dose. If no time is recorded for an assessment, and the assessment takes place at Visit 3, this will be assumed to be a pre-dose assessment.

For laboratory biomarkers, the value at the randomisation visit (Visit 3) will be used as baseline. For those variables assessed at screening (including eosinophils and total immunoglobulin), if the Visit 3 measurement is missing, the screening value will be used as baseline instead. For those variables not assessed at screening, then baseline will be missing.

For sputum and nasal sub-study assessment, the value at the randomisation visit (Visit 3) will be used as baseline. If the Visit 3 measurement is missing or if the sample cannot be assessed, the subject will be excluded from the sub-study.

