- EXA visit is an optional visit and may be initiated when patient experiences COPD exacerbation. Additional assessments can be performed at the discretion of the PI. If the EXA visit falls within +/- 5 days of the scheduled treatment visit window, the laboratory assessments do not need to be repeated at the next scheduled visit if the same laboratory assessments were already completed at EXA visit, unless at the PI's discretion. Refer to Section 8.1.1.5.
- The sponsor will be blinded to the FeNO values except at screening visit, at any repeat testing that is performed during the screening period and prior to Investigational Product (IP) administration.. The sites will be blinded to FeNO values for the whole study duration.
- d Daily Morning Diary: Nocturnal awakening and items related to: Rescue medication use, major/minor symptoms; Daily Evening Diary: EXACT-PRO/E-RSTM: COPD and items related to: rescue medication and maintenance medication. EXACT-PRO/E-RSTM: COPD is completed daily via e-diary and checked at visits.
- Visit 3 spirometry must be performed on the day of randomization prior to IP administration after appropriate restriction are met as per Section 8.1.2. For every other visit, pre-BD spirometry assessments must be performed only after appropriate restrictions are met as per Section 8.1.2, if not this should be rescheduled to the earliest opportunity within the allowed visit window. Applicable for the COVID-19 pandemic: Spirometry should be performed if allowed and according to local regulations and guidance.
- Pre-BD spirometry (according to separate instruction manual) will be performed at EXA visit as part of induced sputum procedures during treatment phase if subject is participating in the sputum sub study.
- The sponsor and site will be blinded to the immunoglobulin, eosinophil, basophil and monocyte counts from the central laboratory reports except screening visits (Visit 1 and 2), any repeat testing that is performed during the screen visits, and prior to IP administration.
- For WOCBP only, urine HCG test to be done at study site at each treatment visit before the IP administration.

- In case of anaphylaxis additional samples will be taken for serum for immunogenicity.
- The ICF must be signed by the subject prior to the collection of optional pharmacogenetic sample.

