- 18. A CAT score of \geq 15 (only based on ePRO questionnaire).
- 19. Stable FEV₁ during the screening period, defined as a change in pre-BD FEV₁ ≤400 mL and/or ≤25% compared to baseline pre-BD (Visit 1) assessment. If a patient demonstrates significant change (>400 mL and/or >25% in either direction) in pre-BD FEV₁ during the screening period, the AZ study physician must be consulted to determine the patient's disposition; randomization may not occur without consultation and agreement with AZ study physician/delegate.

20. Acceptable inhaler and spirometry techniques according to the American Thoracic Society/European Respiratory Society (ATS/ERS) guidelines (Miller et al 2005) during the run-in period.

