6.5.5 COPD Medication Restrictions on the Days of Scheduled Spirometry and FeNO Visits

Spirometry assessments will be performed at the site at scheduled visits (see Table 1 and Table 2). There are restrictions regarding the subject's COPD medications prior to the spirometry assessments. Please see Section 8.1.2.1.

NOTE: Screening (Visit 1 and Visit 2) and Randomization spirometry and FeNO are not allowed without proper medication wash out.

Screening Visit 1 and Visit 2

Screening lung function assessments can only be done when there are no restrictions to medications (also refer to Section 8.1.3) and Visit 1 SARS-CoV-2 naso/oropharyngeal swab test (or rapid test) result is negative. If the SARS-CoV-2 naso/oropharyngeal swab test (or rapid test) result will not be available on the day of Visit 1, the screening lung function

assessments must be postponed until next visit, the postponed Visit 1, after the SARS-CoV-2 naso/oropharyngeal) swab test (or rapid test) result is confirmed negative.

At the postponed Visit 1, the spirometry equipment will allow pre-BD, post-BD spirometry, FeNO and ECG (combined Visit 1 and Visit 2) to be performed. Visit 2 should be scheduled, if the Visit 2 post-BD spirometry and FeNO were not done at the postponed Visit 1. Preferably, Visit 2 should be scheduled no later than 1 week after Visit 1 but the enrolment can be extended to accommodate additional waiting time required to obtain Visit 1 SARS-CoV-2 naso/oropharyngeal swab test result. The subject must meet the COPD medications restrictions in order to perform the lung assessments.

Subjects will be asked to withhold their triple inhaled (ICS/LABA/LAMA) medications on the morning of the screening pre-BD and post-BD spirometry and FeNO (should be at least 12 hours prior to the assessment for twice daily medication and for 24 hours prior to the assessment for once daily medications) for the eligibility assessment (see Section 5.1, inclusion criterion 7). In addition, SABA and SAMA should not be used within 6 hours of this spirometry and FeNO assessment. The subject's usual COPD medications may be administered following completion of the screening lung function procedures.

Treatment Visits 3-15

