9.4.2.5 Forced Expiratory Volume in 1 Second

The change in FEV₁ from baseline to each of the post-randomization visits up to and including the Week 52 visit (Visit 16) will be assessed with change from baseline at week 52 used as the secondary efficacy variable. The last pre-bronchodilator measurement recorded prior to the first dose of IP will be used as baseline FEV₁.

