4.2.5.4 Time to first severe COPD exacerbation

Time to first severe COPD exacerbation through Week 52 will be analysed using a similar model for time to first COPD exacerbation as in Section 4.2.5.1.

4.2.5.5 Change from baseline in pre-dose/pre-BD FEV₁ (L) at Week 52

Change from baseline in pre-dose/pre-BD FEV₁ (L) at Week 52 will be compared between tezepelumab and placebo using a repeated measures analysis on subjects with a baseline pre-dose/pre-BD FEV₁ (L) and at least one non-missing post-randomisation pre-dose/pre-BD FEV₁ (L) value for subjects in the FAS. The dependent variable will be the change from baseline in pre-BD FEV₁ (L) at post-baseline protocol-specified visits (up to the EOT visit). Treatment group will be fitted as the explanatory variable, while region, prior exacerbation count as recorded in IWRS (2, ≥3), visit, baseline pre-dose/pre-BD FEV₁ (L), and the interaction between visit and treatment will be fitted as covariates. Visit will be fitted as a categorical variable, subject will be included in the model using the REPEATED statement (not the RANDOM statement), and the variance-covariance matrix will be assumed to be unstructured. If the procedure does not converge then a compound symmetric variance covariance matrix will be used instead. If the procedure fails to converge with both variance-covariance matrices above, then drop out of covariates will be considered. The Kenward-Roger method will be used in the model to calculate the denominator degrees of freedom, i.e. DDFM=KR. The model is:

*Change in pre-dose/pre-BD FEV₁ (L) = Treatment group + baseline pre-dose/pre-BD FEV₁ (L) + region + prior exacerbation strata + visit + treatment*visit*

This model will be used in two separate Mixed Model Repeated Measures model (MMRM) analyses [assuming missing at random (MAR)], namely:

- The primary analysis will handle intercurrent events as per the primary estimand.
- The supplemental analysis will handle intercurrent events as per the supplemental estimand.

Results will be presented in terms of LSMEANS (with the OBSMARGIN option added), treatment differences in LSMEANS, 95% CI, and p-values for all visits.

Summary statistics of the change from baseline in pre-dose/pre-BD FEV₁ (L) at the study site will be produced by treatment group and visit.

Additional sensitivity analyses to assess the robustness of the repeated measures analysis for pre-dose/pre-BD FEV₁ to missing data are outlined in Appendix 8.2.

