4.2.5.8 COPD assessment tool (CAT)

The CAT total scores and changes from baseline will be summarised by treatment group and visit.

Change from baseline in CAT score through Week 52 will be analysed using a similar model (MMRM) as for the change from baseline in pre-dose/pre-BD FEV₁ (L) described in Section 4.2.5.5. Results will be presented in terms of LSMEANS (with the OBSMARGIN option added), treatment differences in LSMEANS, 95% CI, and p-values for all visits.

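### The FEV1 and CAT repeated-measures models use only one pre-dose reading; adding the screening reading as a separate covariate is an optional and probably modest gain in precision

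*SAP*

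**What the plan says.** For FEV1, SAP 3.1.2 states: "For clinic visit spirometry variables, the latest measurement recorded prior to first dose of study drug will be used as baseline". Protocol 9.4.2.5 has the same rule: "The last pre-bronchodilator measurement recorded prior to the first dose of IP will be used as baseline". A footnote to Table 2 of the protocol adds that "Visit 3 spirometry must be performed on the day of randomization prior to IP administration", so the latest reading is normally Visit 3.

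For CAT, SAP 3.1.2 takes the Visit 3 score and then provides: "If the Visit 3 measurement is missing, the screening value (Visit 1) will be used as baseline instead".

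The FEV1 model in SAP 4.2.5.5 has treatment, region, prior-exacerbation stratum, visit, one baseline FEV1 value "and the interaction between visit and treatment will be fitted as covariates". CAT "will be analysed using a similar model (MMRM) as for the change from baseline in pre-dose/pre-BD FEV"1 (SAP 4.2.5.8). Protocol 9.5.2.2 prints the same FEV1 equation and ties CAT to it.

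Earlier readings are collected in any case. Protocol Table 1 schedules pre-BD spirometry at Visits 1 and 2, and CAT at Visit 1. Inclusion criterion 19 judges FEV1 stability "compared to baseline pre-BD (Visit 1) assessment". Inclusion criteria 8 and 18 require a CAT score of at least 15 at Visit 1 and again before randomisation, both on the ePRO questionnaire. Protocol 4.1 allows Visits 1 and 2 to be combined, so a separate Visit 2 FEV1 exists for some subjects only.

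**The concern.** A single spirometry or questionnaire reading carries day-to-day variation. A second pre-randomisation reading of the same measure usually helps to predict the Week 52 value. If it does, a model that includes it gives a narrower interval for the treatment difference. The SAP already follows this idea elsewhere: the baselines for E-RS, EXACT-PRO, rescue use and night awakenings are means over 7 or 14 days (SAP 3.1.2). Those endpoints are exploratory, whereas change in FEV1 and in CAT are secondary.

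At stake is the width of two secondary confidence intervals in a trial sized only for exacerbations. SGRQ is not part of this point, because it is not measured at screening.

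**Working it through.** **The plan's own figures.** The documents give no power, SD or correlation for FEV1 or CAT. The only sizing is for the primary endpoint (SAP 1.3): placebo rate 1.6, rate ratio 0.70, dispersion 0.6, one-sided 5%. I read 10% uniform drop-out as a mean exposure of 0.95 year.

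n per arm = (1.645 + 0.842)² × [(1/1.6 + 1/1.12)/0.95 + 2 × 0.6] / (ln 0.70)² = 135.97, so 136, as stated. Power at 141 per arm is 81.25% (stated 81.2%). With a placebo rate of 1.2 and 169 per arm it is 81.5% before the futility loss. These figures reproduce, and nothing below touches them.

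**Similarity of conditions.** Protocol 6.5.5 says: "Screening (Visit 1 and Visit 2) and Randomization spirometry and FeNO are not allowed without proper medication wash out". Protocol 8.1.2.1 requires a 06:00–11:00 start at screening and at randomisation. It also requires every later spirometry to fall within 1.5 hours of the time of the randomisation reading, so Week 52 is matched to Visit 3 and not to Visit 1 or 2.

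**Formula.** With the Visit 3 value in the model, the residual variance of the change score equals that of the Week 52 value. Let r be the correlation between two pre-randomisation readings, q3 and q1 the correlations of Visit 3 and Visit 1 with Week 52. All three are assumed.

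- Visit 3 alone: residual variance 1 − q3².
- Visit 1 and Visit 3 as two covariates: 1 − (q3² + q1² − 2·r·q1·q3)/(1 − r²).
- Equal q, mean of m readings: 1 − m·q²/(1 + (m − 1)·r).

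Example with r = 0.90, q1 = q3 = 0.80: (1 − 2 × 0.64/1.90)/(1 − 0.64) = 0.326/0.360 = 0.906.

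Variance ratios against Visit 3 alone:

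| Assumption | Ratio | SE ratio |
|---|---|---|
| r 0.90, q3 0.80, q1 0.80 | 0.906 | 0.952 |
| Same, three readings (Visits 1 and 2 separate) | 0.873 | 0.934 |
| r 0.90, q3 0.80, q1 0.78 | 0.947 | 0.973 |
| r 0.85, q3 0.70, q1 0.67 | 0.960 | 0.980 |
| r 0.80, q3 0.60, q1 0.57 | 0.965 | 0.982 |
| r 0.90, q3 0.80, q1 0.72 | 1.000 | 1.000 |

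The last row is the limiting case: q1 = r × q3 (0.72 = 0.90 × 0.80), so Visit 1 adds nothing once Visit 3 is known. There, replacing the baseline covariate by the plain mean of the two readings gives (1 − 0.76²/0.95)/0.36 = 0.392/0.36 = 1.089, a loss of 9%. Two separate covariates lose nothing.

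**Effect of the eligibility cuts.** Selection on these readings changes their correlation, so the cuts were simulated (1,000,000 draws, q1 = q3 = q).

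- CAT of at least 15 at both visits (assumed mean 19, SD 7), with r 0.7–0.8 and q 0.6–0.7 before selection: ratios 0.874–0.950.
- FEV1 change within 400 mL and within 25% (assumed mean 1.2 L, SD 0.5 L), with r 0.8–0.9 and q 0.8–0.9 before selection: ratios 0.874–0.951.

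After selection the gain is therefore 5–13% if Visit 1 predicts as well as Visit 3, and it shrinks towards zero as Visit 1 predicts less well. Without the cuts, one more favourable setting (r 0.85, q 0.80 at both visits) gives 0.856. In the simulation the FEV1 cuts raised r from 0.80 to 0.92 and from 0.90 to 0.94, so the post-selection figures are the ones to use.

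**Limits of the calculation.** The formulas treat Week 52 alone, while the SAP model fits one baseline slope across visits. Criterion 19 was applied as a hard cut on both limits, although the protocol words it as and/or and lets the sponsor's study physician agree to randomisation.

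**The case against.** The case for leaving the model alone is good. The protocol and SAP agree, the baseline is fully defined, and adjusting for the baseline of the change score is valid and unbiased. Visit 3 is the reading matched in clock time to Week 52. Between Visit 1 and Visit 3 a subject may have a treated exacerbation or respiratory infection (protocol 5.4), a run-in extended by 28 days (protocol 4.1), an ICS device switch (inclusion criterion 7) or a stop of roflumilast (protocol Table 6). Each of these makes Visit 1 less predictive. If correlations decay with time (FEV1 r 0.81–0.89, q 0.53–0.72; CAT r 0.65–0.70, q 0.39–0.54, also assumed), the variance fall with two readings is about 1–10% for FEV1 and 3–8% for CAT. All p-values beyond the primary are nominal (SAP 4.1.2), and no decision rule in the documents depends on these intervals.

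All of that stands, and it limits both the size and the priority of the point. It does not remove the point: a pre-randomisation covariate cannot bias the comparison, and entering it separately lets the model give it little weight where it predicts poorly.

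Three stronger readings might be inferred and are not supported:

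- **That earlier FEV1 readings are thrown away.** The latest-reading rule makes them the fallback if Visit 3 is missing, as for CAT.
- **That all readings are taken under the same conditions.** Washout and the morning window are shared, but the 1.5-hour matching is not.
- **That gains near 30% are available.** With r = q = 0.85 and three readings the ratio is 0.711, but this supposes that readings weeks apart agree no better than readings a year apart. Three readings also exist only where Visits 1 and 2 were separate, and the documents do not give that share.

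**Conclusion.** The point holds as an optional efficiency improvement. The FEV1 and CAT models use one pre-dose reading, while essentially every randomised subject has at least one more that could enter as a covariate. The expected fall in Week 52 variance is roughly 0–13%, which makes the standard error about 0–7% smaller (√0.874 = 0.935 at the upper end). At that upper end, 338 subjects would carry the information of about 338/0.874 = 387 for these endpoints; at the lower end nothing is gained. The range rests entirely on assumed correlations, means and SDs, because the documents supply none.

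A reader might take this as a flaw in the analysis. It is not: there is no bias, no contradiction between the documents, and no effect on the primary endpoint, its sample size or its alpha.

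**What to change.** - Keep the Visit 3 value as the baseline for the change score.
- In SAP 4.2.5.5, add the screening pre-BD FEV1 (Visit 1, or the mean of Visits 1 and 2 where they were separate) as its own covariate. In SAP 4.2.5.8, add the Visit 1 CAT score. Do not average either with Visit 3.
- If the screening value is missing, use the subject's Visit 3 value. This relies on pre-randomisation data only.
- Carry the FEV1 covariate into the FEV1 subgroup models (SAP 4.2.5.5) and the FEV1 multiple-imputation models (SAP Appendix 8.2).
- SAP section 6 now states that there are no changes from the protocol. Record there the departure from the model printed in protocol 9.5.2.2, before primary database lock.

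The cost is 1 degree of freedom per model, some reprogramming and a declared departure from the protocol's equation. No new data are needed.
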